#### Primary outcome:

**Specific aim 1:** The objective of this investigation is to identify the clinical effectiveness of sub-dissociative dose IV Ketamine as an adjunctive treatment for the acutely suicidal patient in the ED.

**Hypothesis 1:** There will be a clinically significant decrease in suicidal ideation (SI) in those treated with Ketamine after 24 hours.

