#### Secondary outcomes:

**Specific aim 2:** Determine if this protocol for ketamine holds its effectiveness over time post infusion.

**Hypothesis 2:** The effects of ketamine can last up to a week post infusion.

Primary outcome measures of SI will be through self-administered Beck Scale for Suicidal Ideation (BSS or BSSI or SSI). The self-administered version of Montgomery- Åsberg Depression Rating Scale (MADRS) will be used to measures degree of concomitant depression symptoms. These patient-level data will serve as baseline comparatives. Subjects shall be randomized by the pharmacy and designated to either ketamine treated or saline placebo arm, with both the treating nurse and physician blinded. The experimental arm shall receive 0.5 mg/kg IV ketamine infusion over 40 minutes. To test for effectiveness within groups, we will measure outcomes at two different time points, 4 and 24 hours post infusion. To evaluate effectiveness between groups we will compare results between treatment and placebo arms. To test for specific aim 2, and to maximize response rate, a phone call will be made, one week after the initial questionnaire was done.

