#### RESEARCH DESIGN/METHODS/SUBJECT JUSTIFICATION

##### General Approach

This study will be conducted in the ED. The investigative team will notify the ED that this research is underway. Emergency Department staff will be given an informational brief regarding the nature, purpose and scope of the research protocol. The brief will be distributed digitally via email, and will be discussed in staff meetings and huddles to reach 100% of staff. Healthcare personnel who wish to participate will be given a script and check list for exclusion criteria. If a physician feels that a patient may be eligible for participation he/she can refer the patient to the research team for additional evaluation and approach regarding the research study." The role of this individual is only for recruitment purposes and will not be involved in any other activities of the protocol or informed of patient information pertaining to the research.

Participants will be adults, whom are 18 years or older, military personnel or civilians eligible for care in the military treatment facility. This study aims to test for a clinically significant decrease in SI in the acutely suicidal patient. Repeat measures over time will be conducted at two subsequent

time points. To determine week long lasting effects of treatment, a third repeat measure will be conducted. All time point collections will be done for both arms.

The trial is designed as a double-blinded Randomized Control Trial (RCT) with two arms, Experimental vs. Placebo. This trial will mask patients, health providers, and outcome assessors to avoid ascertainment bias; the only unblinded participants will be the pharmacy, which will not affect the blinding, because at our institution they do not decide on patient disposition. This study design is not only necessary to demonstrate the effectiveness as a treatment for the acutely suicidal patient, but also to validate and add power to studies supporting anti-suicidal properties of ketamine. Outcomes will be measured by Psychometric testing (BSSI & MADRS-S). With the exception of the aforementioned experimental procedure, which will be done prior to transfer to inpatient units, both arms will then be treated in accordance to usual management for suicidal patients, which for both arms includes inpatient admission, therapy, and possible initiation of antidepressants.

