## Experimental Procedure

1. Baseline evaluation of suicidal severity (BSSI) & degree of depressive symptoms (MADRS-S) will be evaluated through self-administered questionnaires.
2. The experimental and placebo arms will receive a single dose of IV ketamine, 0.5 mg/kg in 100 cc NS or 100 cc of NS infused over 40 minutes.
3. Post ketamine re-evaluation of outcome measures at four and twenty-four hours will determine clinical effectiveness of ketamine intervention
4. Inspection of admission and transfer time provides time measurement for LOS. This secondary measure is needed to determine efficiency of intervention.
5. Post ketamine re-evaluation of outcome measure at one-week post infusion will elucidate ketamine's durability of effect.

**Table 2:** Description of activities at time points during the study

|  | Study Visit 1
Baseline ( $t_0$ ) | Study Visit 1
4 hours ( $t_1$ ) | Study Visit 1
24 hours ( $t_2$ ) | Study Visit 2
1 week ( $t_3$ ) |
|--|-------------------------------------|------------------------------------|-------------------------------------|-----------------------------------|
|  |                                     |                                    |                                     |                                   |

|  |   |   |   |   |
|--|---|---|---|---|
| Eligibility review and confirmation                    | X |   |   |   |
| Education regarding research & Informed Consent signed | X |   |   |   |
| History & Physical                                     | X |   |   |   |
| Randomization  | X |   |   |   |
| Dispense study drug                                    | X |   |   |   |
| IV Ketamine  | X |   |   |   |
| Vital Signs & ADR* monitored                           | X | X | X |   |
| Review adverse events                                  | X | X | X |   |
| Psychometric testing                                   | X | X | X | X |

\*ADR: Adverse drug reaction

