**STATISTICAL ANALYSIS**

All data analysis will be carried out using SPSS ® Version 25. Tableau Desktop 2018.1 will be used to augment the creation of graphs. See 3.7.C for power calculation and sample size derivation. If subjects do not complete a baseline, they will not be incorporated in the analysis. A recent clinical study validated that an average of four items from the SSI, with a cut-off of  $\geq 2$ , is sufficient in classifying patients as high risk vs. low risk. Therefore, any patient who does not complete at least four items on the SSI during each of the post administration time points will be excluded from the study. Missing data will be excluded from analysis as long as the degree of freedom permits. The type of data analysis will be in accordance to the Test plan, Table 6. Each arm of the trial will be considered a "group." Appendix D: Sample Data Collection Sheet describes demographic data points as well as measurement scale of each of the below variables. Stratification factors will be accounted for as a covariate in multivariate models.

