### 11.6 Data Analysis Plan: Complete description: Background, Objectives, Design, Step by Step how the project is going to be done, Data analysis plan:

**Table 6:** Test Plan of Data Analysis

| Question to be answered   | Type of Analysis                                   | Independent (x)  | Dependent (y)      | Relationship     |
|---|--|--|--------------------|------------------|
| Is there a difference effect of ketamine in those who are high suicide vs. high depressed?                  | McNemar test                                       | High Suicide   | High depressed     | Within           |
| Is there a difference in the placebo between the same two groups?   | McNemar test                                       | High Suicide group                                     | High Suicide group | Within           |
| Is there any difference between ketamine vs. placebo on BSSI & MADRS?                                       | One-way MANOVA                                     | Group  | BSSI; MADRS        | Between          |
| Is there a difference in SI between Ketamine vs placebo   | 2 Independent sample t test                        | Group  | BSSI @ T4          | Between          |
| Is there a difference in depression between Ketamine vs placebo   | 2 independent sample t test                        | Group  | MADRS @ T4         | Between          |
| Is there a difference in effect from placebo when accounting for covariates?                                | MANCOVA  | Fixed factor: Group
Covariates: Demographics        | BSSI, MADRS @ T4   | Between          |
| Is there a difference in effect from ketamine @ the different time points?                                  | Mixed model
Or
Repeated measure ANOVA | Fixed factor: Group                                    | BSSI               | Within & between |
| Is there a difference in group at the different time points, when MADRS is a covariate?                     | Mixed model                                 | Fixed factor: Group
Covariates: MADRS               | BSSI               | Within & between |
| Is there a difference in group at the different time points, when MADRS, and demographics are considered? * | Mixed model                                 | Fixed factor: Group
Covariates: MADRS, demographics | BSSI               | Within & between |

\*This case requires a larger sample size.

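### The primary hypothesis names no comparator, and no planned ketamine-versus-placebo test is designated to decide it or clearly placed at 24 hours

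*Combined protocol and SAP*

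**What the plan says.** Section 9.3, under the primary outcome, gives Hypothesis 1 as: "There will be a clinically significant decrease in suicidal ideation (SI) in those treated with Ketamine after 24 hours". Under the secondary outcomes, Hypothesis 2 is: "The effects of ketamine can last up to a week post infusion". Neither mentions placebo.

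The same section assigns the two early assessments to a within-group purpose: "To test for effectiveness within groups, we will measure outcomes at two different time points, 4 and 24 hours post infusion". The next sentence adds the controlled comparison, without a time point: "To evaluate effectiveness between groups we will compare results between treatment and placebo arms".

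Section 10.1, Experimental Procedure, item 3 states: "Post ketamine re-evaluation of outcome measures at four and twenty-four hours will determine clinical effectiveness of ketamine intervention". Item 5 uses similar language for durability at one week.

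The General Approach describes care after the infusion, "which for both arms includes inpatient admission, therapy, and possible initiation of antidepressants". Section 14.4 considers a small placebo benefit likely, and the limitations in section 10.1 list the placebo effect.

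Table 6 in section 11.6 asks "Is there a difference in SI between Ketamine vs placebo" and answers it with a two-sample t test on BSSI at a time point labelled T4. Table 2 labels the assessments t0 (baseline), t1 (4 hours), t2 (24 hours) and t3 (one week).

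**The concern.** Patients enter during an acute crisis, and every one of them is then admitted and treated. SI would be expected to fall in both arms, whatever is in the infusion bag. A hypothesis that asks only for a fall among ketamine patients can therefore be met when placebo patients improve just as much. The placebo arm is there to separate the drug effect from that background change, yet the primary claim as worded makes no use of it.

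Table 6 does contain the comparison that is needed. The trouble is that nothing links Hypothesis 1 to a particular row. At analysis, a reader could not tell whether a fall within the ketamine arm, a between-arm difference at some other time, or a between-arm difference at 24 hours settles the primary question.

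**Working it through.** **1. Which planned analysis could decide Hypothesis 1?** The Table 6 rows with BSSI as an outcome are:

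| Row | Contrast | Time point |
|---|---|---|
| One-way MANOVA (BSSI, MADRS) | Between | None given |
| Two-sample t test (BSSI) | Between | T4, undefined |
| MANCOVA (BSSI, MADRS) | Between | T4, undefined |
| Mixed model or repeated measures ANOVA | Within and between | All; no 24-hour contrast stated |
| Two mixed models with covariates | Within and between | All; no 24-hour contrast stated |

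No row is marked as primary. T4 might mean four hours, or the fourth assessment (one week); neither is 24 hours. The first repeated-measures row lists only Group as a fixed factor. Section 11.5 makes the linear model for repeated measures conditional on reaching 74 subjects, while 62 are planned. Hypothesis 1 asks for a clinically significant decrease, but no rule says what would meet that. The only purely within-arm rows are the two McNemar tests. No row is a paired test of BSSI change in the ketamine arm.

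**2. The plan's own sample size.** Inputs from section 11.5 are alpha 0.05, power 0.80 and d = 0.8. Sidedness is not stated. A two-sided two-sample t test (noncentral t) gives 25.52 per arm, matching the stated 25.5; one-sided would give 20.0. The stated 28.2 for correlations is reproduced at r = 0.5 (28.25; r is my assumption). Then 2 × 28 = 56. Adding 10% gives 56 × 1.1 = 61.6, which rounds up to 62; dividing instead gives 56 / 0.9 = 62.2. The stated 62 is reproduced, and its t-test component is a between-arm comparison.

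**3. Illustration of the literal reading.** Suppose Hypothesis 1 were judged by a paired t test in the ketamine arm, and ketamine did nothing. The documents give no size for the background fall, so I assume a range, in SDs of change (dz). Ten percent dropout leaves 31 × 0.9 = 27.9, about 28. The noncentrality is dz × √n; for example, 0.5 × √28 = 2.65. Chance of a significant result at two-sided 0.05:

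| Assumed fall (dz) | n = 28 | n = 31 |
|---|---|---|
| 0.2 | 17.5% | 19% |
| 0.3 | 33% | 37% |
| 0.5 | 72% | 77% |
| 0.8 | 98% | 99% |

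With the same fall in both arms (28 per arm, 40,000 simulated trials per setting), the between-arm t test was significant about 5% of the time, and about 2.5% of the time in ketamine's favour, whatever the size of the fall.

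**4. Does a between-arm primary test need more patients?** The noncentrality is d × √(n/2). At d = 0.8:
- 31 per arm: 0.8 × √15.5 = 3.15, power 87%.
- 28 per arm: 0.8 × √14 = 2.99, power 84%.

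Both exceed the planned 80%.

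**The case against.** The strongest reply is that this is a placebo-controlled trial in design and analysis, and that loose phrasing does not change that. Section 9.3 states the between-arm comparison directly after the within-group sentence. Section 9.2 says the effects are studied against saline. The General Approach collects all time points in both arms and ties the demonstration of effectiveness to the blinded two-arm design. Several Table 6 rows compare arms, and Table 4 sizes the trial that way. Within groups is plural and section 11.1 defines each arm as a group, so that wording covers placebo too. The Experimental Procedure items are steps in a list rather than decision rules.

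All of this stands, and it rules out three stronger readings that a reader might reach:

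- **That the hypotheses will be judged on ketamine patients alone.** The documents do not say so; the placebo comparison is planned.
- **That 33%, 72% and 98% are error rates of this trial.** They belong to a paired test that Table 6 does not contain, under a background fall that is assumed. Section 14.4 expects only a small placebo benefit, although that statement does not cover the effect of admission and therapy.
- **That Hypothesis 2 cannot be refuted because it says up to a week.** Section 9.2 words it as an effect still seen at one week, and the one-week assessment in both arms can contradict that. Hypothesis 2 lacks a comparator; it is not worded as change in the ketamine arm alone.

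The reply does not supply the missing link. It identifies no between-arm analysis that decides Hypothesis 1, and none clearly placed at 24 hours.

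**Conclusion.** The concern holds as a mismatch between the hypotheses and the analysis plan. Hypothesis 1 is worded as a before-after fall in one arm, and the planned placebo contrasts are not tied to it. Its literal criterion can be met without a drug effect, because background improvement is likely in both arms.

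The size of the risk depends on two assumptions that the documents do not settle: that a paired within-arm test would be used, and how large the background fall is. On those assumptions the chance of a misleading positive runs from 17.5% at 0.2 SD to 98% at 0.8 SD with 28 patients. A between-arm test removes this dependence on the background fall. The conclusion on wording and designation rests on the text alone and needs neither assumption.

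This should be settled before analysis, because it determines what the trial may claim.

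**What to change.** 1. Restate Hypothesis 1 as lower BSSI with ketamine than with placebo at 24 hours (t2), and Hypothesis 2 as the same contrast at one week (t3). If the term clinically significant is kept, give it a rule.
2. Name one between-arm Table 6 analysis of BSSI at t2 as the test that decides Hypothesis 1. The two-sample t test row is the closest match to the sample size calculation.
3. Replace T4 throughout Table 6 with the Table 2 labels.
4. Reword the within-groups sentence in section 9.3 and items 3 and 5 of the Experimental Procedure so that within-arm change is descriptive only.

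This is a change of wording, with no new visits, data or patients. N = 62 can stay at the plan's d = 0.8; at d = 0.5, between-arm power would be only 49% with 31 per arm or 45% with 28. The cost is that a fall within the ketamine arm can no longer be claimed as success.

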#### Secondary outcomes:

**Specific aim 2:** Determine if this protocol for ketamine holds its effectiveness over time post infusion.

**Hypothesis 2:** The effects of ketamine can last up to a week post infusion.

Primary outcome measures of SI will be through self-administered Beck Scale for Suicidal Ideation (BSS or BSSI or SSI). The self-administered version of Montgomery- Åsberg Depression Rating Scale (MADRS) will be used to measures degree of concomitant depression symptoms. These patient-level data will serve as baseline comparatives. Subjects shall be randomized by the pharmacy and designated to either ketamine treated or saline placebo arm, with both the treating nurse and physician blinded. The experimental arm shall receive 0.5 mg/kg IV ketamine infusion over 40 minutes. To test for effectiveness within groups, we will measure outcomes at two different time points, 4 and 24 hours post infusion. To evaluate effectiveness between groups we will compare results between treatment and placebo arms. To test for specific aim 2, and to maximize response rate, a phone call will be made, one week after the initial questionnaire was done.

### 9.4 Study Design:

Describe study design in one to two sentences (e.g., prospective, use of existing records/data/specimens, observational, cross-sectional, interventional, randomized, placebo-controlled, cohort, etc.). Specify the phase – Phase I, II, III, or IV – for FDA-regulated investigational drug research

This study is designed as an RCT with two arms, Experimental vs. Placebo. Table 1 shows a detailed description of both arms. This will be a triple masked study. The patient, healthcare providers, and outcomes assessor will be blinded.

**Table 1:** Description of Experimental Arms

| Arm                              | Intervention/Treatment  |
|----------------------------------|---|
| Experimental:
Ketamine | Drug: Ketamine (Ketalar)
Single dose IV ketamine, 0.5 mg/kg in 100 cc Normal Saline, infused over 40 minutes
Other Name: N-methyl-D-aspartate (NMDA) glutamate receptor antagonist |
| Placebo: Saline           | Drug: Normal Saline (NS)
100 cc infused over 40 minutes   |

## 9.5 Target Population:

Describe the population to whom the study findings will be generalized

Suicidal behavior is complex and affects all age groups, with the highest prevalence in those that are middle aged (45-54 years old). With this said it is the 4th leading cause of death in those 35 to 44 years old. <35 years old it is the second leading cause of death. Therefore, the selected subject population reflects any adult that could present to the ED. Children and adolescents (< 18 years old) are excluded to mitigate the variabilities their developing brain would introduce into the study.

## 9.6 Benefit to the DoD:

State how this study will impact or be of benefit to the Department of Defense

Suicide is an enormous burden on the active duty service member's operational readiness, as it has the potential to permanently take the member out of the fight. The rippling effects, of this individual action, not only affects moral of that sailor or marine's unit, but it also has profound impacts on the friends, coworkers, and, most importantly, their family. This study has the potential to provide additional intervention treatment literature.

## 10.0

### Study Procedures, Data Management, and Privacy

#### 10.1 Study Procedures:

Describe step-by-step how the study will be conducted from beginning to end

#### RESEARCH DESIGN/METHODS/SUBJECT JUSTIFICATION

##### General Approach

This study will be conducted in the ED. The investigative team will notify the ED that this research is underway. Emergency Department staff will be given an informational brief regarding the nature, purpose and scope of the research protocol. The brief will be distributed digitally via email, and will be discussed in staff meetings and huddles to reach 100% of staff. Healthcare personnel who wish to participate will be given a script and check list for exclusion criteria. If a physician feels that a patient may be eligible for participation he/she can refer the patient to the research team for additional evaluation and approach regarding the research study." The role of this individual is only for recruitment purposes and will not be involved in any other activities of the protocol or informed of patient information pertaining to the research.

Participants will be adults, whom are 18 years or older, military personnel or civilians eligible for care in the military treatment facility. This study aims to test for a clinically significant decrease in SI in the acutely suicidal patient. Repeat measures over time will be conducted at two subsequent

time points. To determine week long lasting effects of treatment, a third repeat measure will be conducted. All time point collections will be done for both arms.

The trial is designed as a double-blinded Randomized Control Trial (RCT) with two arms, Experimental vs. Placebo. This trial will mask patients, health providers, and outcome assessors to avoid ascertainment bias; the only unblinded participants will be the pharmacy, which will not affect the blinding, because at our institution they do not decide on patient disposition. This study design is not only necessary to demonstrate the effectiveness as a treatment for the acutely suicidal patient, but also to validate and add power to studies supporting anti-suicidal properties of ketamine. Outcomes will be measured by Psychometric testing (BSSI & MADRS-S). With the exception of the aforementioned experimental procedure, which will be done prior to transfer to inpatient units, both arms will then be treated in accordance to usual management for suicidal patients, which for both arms includes inpatient admission, therapy, and possible initiation of antidepressants.

Suicidal patients, subjectively identified by clinician, upon admission to the ED will be medically cleared by the EM physician, and then meet with the mental health liaison to be screened for admission to the psychiatric department, per normal standard of care. Study investigators will not be available around the clock, but when available will begin the pre-screening method for this investigation. The treating physician will pre-screen them for inclusion and exclusion criteria per an IRB approved check list (Appendix D: Criteria Checklist).

The patient will be approached for informed consent in accordance to with 21 CFR 50. They will be provided with a written document that embodies the elements of the informed consent. The consent will be presented orally to the subject with a witness. Once presented the subject will be given a reasonable time to review the contents and inquire information. Upon signing of the form, a copy shall be given to them.

Once consent is obtained, they will be presented with a paper form to complete the BSSI and MADRS-S. These measures will serve as baseline severity of suicidal wishes and plans, and degree of depression symptoms. Questionnaires will be stored in locked drawer's in the locked office the Division Officers in the Emergency Department, the Inpatient Mental Health ward, or the study coordinator.

Once the patient is deemed medically cleared by the treating physician, the study treatment will be ordered by an ED provider, per the randomization schedule, and administered by an ED nurse (Please see below for more detailed methodology). Those in the experimental arm will be treated with 0.5 mg/kg IV infusion of ketamine over 40 minutes. Those in the control arm will be treated with 100 cc Saline infusion over 40 minutes. (Table 1) Since there are no pharmaceutical treatment specific for acute suicide, it is in accordance to the Declaration of Helsinki (DOH) to utilize a saline placebo control. Vitals will be checked every 5 minutes during infusion. Questionnaires will be repeated at four time points for both arms, once in the ED before drug administration, one at 4 (+/-1) hours post-infusion, whether in the ED or the psychiatric unit, another 24-36 hours after the infusion in the inpatient psychiatric unit, and lastly one-week (+1 day) post treatment by phone call.

